3.1. Randomization

3.1.1. Part 1

A total of 20 participants with moderate or severe cGVHD will be randomized 1:1 to itacitinib 200 mg QD plus corticosteroids or 300 mg QD plus corticosteroids.

3.1.2. Part 1 Expansion

A total of up to 140 participants (35 per treatment group) with moderate or severe cGVHD will be randomized 1:1 to 1 of 4 treatment groups: itacitinib 300 mg QD plus corticosteroids (Treatment Group A), itacitinib 400 mg QD plus corticosteroids (Treatment Group B), itacitinib 300 mg BID plus corticosteroids (Treatment Group C), or corticosteroids monotherapy (Treatment Group D).

Randomization will be stratified by cGVHD risk status (moderate vs severe). Treatment Groups B and C will have an initial safety run-in of 10 participants to determine safety and tolerability of the dose before expanding (see definition of DLT in Section 6.1.1.3 of the Protocol). Participants enrolled in the safety run-in will be monitored continuously using the Bayesian approach. Treatment Group C was discontinued as of Amendment 8, and participants in that treatment group who were ongoing were allowed to reduce to 400 mg QD plus corticosteroids.

3.2. Control of Type I Error

No formal statistical tests will be performed in Part 1 and Part 1 expansion. All CIs will be 95%.

3.3. Sample Size Considerations

3.3.1. Part 1

In Part 1, approximately 20 participants will be enrolled to achieve 10 randomly assigned participants in each of the 2 dose groups of itacitinib in order to identify an optimal dose for further study. This sample size was chosen based on typical Phase 1 studies employing a 3 + 3 design that enroll up to 9 participants in order to identify recommended Phase 2 doses. A sample size of 20 participants (10 per treatment group) allows for concurrent enrollment at 2 dose levels

that have been previously characterized in other disease settings and is expected to enable the clinical characterization of study treatment across 2 treatment cohorts. No formal statistical comparison will be performed between treatment groups.

3.3.2. Part 1 Expansion

Sample size in Part 1 expansion is based on clinical feasibility and consideration. No hypothesis test is planned for efficacy. Up to 35 participants will be enrolled into each treatment group. The toxicity of itacitinib will be monitored continuously for Treatment Groups B and C using a Bayesian approach. A total of up to 140 participants will be enrolled into Part 1 expansion of the study. Regarding the key secondary endpoint, Month 6 response rate, a table of Bayesian posterior probabilities and related descriptions are provided below. This posterior probability may be used to support decision-making on itacitinib dosing/schedule for Part 2, including decisions made by the DMC

[figure not shown]
Table 3 presents Bayesian posterior probability of demonstrating a clinically meaningful treatment difference [REDACTED] in Month 6 response rate between any itacitinib group and the corticosteroids-only group under various response rates at the end of the expansion.

Table 3: Bayesian Posterior Probability to Demonstrate That There Is a Clinically Meaningful Difference [REDACTED] Between Any Itacitinib Group and the Corticosteroids-Only Group

| Responders in an Itacitinib Group (out of 35) | Responders in Corticosteroids-Only Group (out of 35) | | | | |
|--|--|-------|-------|-------|-------|
| | 18 | 19 | 20 | 21 | 22 |
| 25 | 64.3% | 54.8% | 45.0% | 35.3% | 26.4% |
| 26 | 73.1% | 64.4% | 54.9% | 44.8% | 35.0% |
| 27 | 80.9% | 73.4% | 64.7% | 54.9% | 44.7% |
| 28 | 87.2% | 81.3% | 73.9% | 65.0% | 55.0% |
| 29 | 92.1% | 87.7% | 81.9% | 74.4% | 65.3% |
| 30 | 95.5% | 92.6% | 88.4% | 82.6% | 75.0% |

Note: With a binomial likelihood, binomial (n, p) with s number of responders out of n participants, and a beta prior, Beta (a, b), the posterior is calculated as Beta(a+s, b+n-s).

Interpretation:

3.4. Schedule of Assessments

Refer to Protocol Amendment 8 dated 30 SEP 2021 for a full description of all study procedures and assessment schedules for this study.

4. DATA HANDLING DEFINITIONS AND CONVENTIONS

4.1. Scheduled Study Evaluations and Study Periods

4.1.1. Day 1

Day 1 is the date that the first dose of itacitinib is administered to the participants. For the corticosteroids-only group, Day 1 will be defined as the first nonmissing dose day.

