^c Every 28 days (± 7 days) up to 1 year (D364) from Day 1 and then every 8 weeks (± 7 days) up to 2 years from Day 1.

d Chimerism testing can be performed on Day 1 before study drug administration. Results are not required for randomization and treatment.

^e Chronic GVHD staging (see criteria in Appendix C) performed at screening will be used for eligibility assessment and stratification purposes

f Chronic GVHD organ score and overall severity score 0 to 10 (see criteria in Appendix E) will be performed on Day 1, and this will be the baseline for cGVHD response assessment during treatment and post-treatment follow-up.

g FEV1% performed within 7 days of Day 1 can be used for cGVHD response assessment if bronchiolitis obliterans was not diagnosed at screening.

h May be performed within 7 days of Day 1. If liver cGVHD is diagnosed at screening, total bilirubin, ALT, and ALP should be repeated on Day 1.

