5.1. Inclusion Criteria

Participants are eligible to be included in the study only if all of the following criteria apply:

- 1. Male or female, aged 18 years or older inclusive at the time of signing the ICF.
- 2. Active, clinically diagnosed, moderate or severe cGVHD per NIH Consensus Criteria (Jagasia et al 2015; Appendix C):
 - a. Moderate cGVHD: At least 1 organ (except lung) with a score of 2, 3 or more organs involved with a score of 1 in each organ, or lung score of 1.
 - b. Severe cGVHD: At least 1 organ with a score of 3, or lung score of 2 or 3.

Note: Candidates who transition from active aGVHD to cGVHD without tapering off of corticosteroids (< 0.25 mg/kg per day methylprednisolone or equivalent) \pm CNI are also eligible.

- 3. Underwent allo-HCT from any donor HLA type (related or unrelated donor with any degree of HLA matching) using any graft source (bone marrow, peripheral blood stem cells, or cord blood). Recipients of myeloablative, nonmyeloablative, or reduced intensity conditioning are eligible.
- 4. KPS score $\geq 60\%$.
- 5. Evidence of myeloid and platelet engraftment, that is, ANC $\geq 1.0 \times 10^9/L$ and platelet count $\geq 50 \times 10^9/L$. *Note:* Use of growth factor supplementation and transfusion support is allowed during the study; however, transfusion to reach a minimum platelet count for inclusion is not allowed within the 7 days before the screening laboratory assessment.
- 6. Willingness to avoid pregnancy or fathering children based on the criteria below.
 - a. Men must agree to take appropriate precautions to avoid fathering children (with at least 99% certainty) from screening through 90 days after the last dose of study drug(s)/treatment and must refrain from donating sperm during this period. Permitted methods that are at least 99% effective in preventing pregnancy (see Appendix A) should be communicated to the participants and their understanding confirmed.
 - b. Women of childbearing potential must have a negative serum pregnancy test at screening and before the first dose on Day 1 and must agree to take appropriate precautions to avoid pregnancy (with at least 99% certainty) from screening through safety follow-up. Permitted methods that are at least 99% effective in preventing pregnancy (see Appendix A) should be communicated to the participants and their understanding confirmed.

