5.2. Exclusion Criteria

Participants are excluded from the study if any of the following criteria apply:

- 1. Has received more than 1 prior allo-HCT. Prior autologous HCT is allowed.
- 2. Has received more than 3 days/72 hours of systemic corticosteroid treatment for cGVHD.
- 3. Has received any other systemic treatment for cGVHD, including ECP. CNIs initiated before randomization may be continued at the same or lower dose; topical/inhaled steroids are acceptable.
- 4. Prior treatment with a JAK inhibitor within 8 weeks before randomization. Participants who received a JAK inhibitor for aGVHD are eligible only if they achieved CR or PR.
- 5. Removed in Amendment 6.
- 6. Presence of active uncontrolled bacterial, fungal, parasitic, or viral infection. Infections are considered controlled if appropriate therapy has been initiated and, at the time of screening, no signs of infection are present.
- 7. Active HBV or HCV infection that requires treatment, or at risk for HBV reactivation (ie, positive HBsAg). Participants with negative HBsAg and positive total HBc antibody may be included if HBV DNA is undetectable at the time of screening. Participants who are positive for HCV antibody are eligible only if PCR is negative for HCV RNA. Participants whose immune status is unknown or uncertain must have results confirming immune status before enrollment. Prior serology results are acceptable for determining eligibility.
- 8. Known HIV infection.
- 9. Evidence of relapsed primary hematologic disease, or receipt of treatment for relapse after the allo-HCT was performed, including DLIs for the treatment of molecular relapse.
- 10. Maintenance therapy for the primary hematologic disease started within 4 weeks before initiation of study treatment (Day 1) or plans to start maintenance therapy after Day 1.
- 11. Corticosteroid therapy at doses > 0.25 mg/kg per day methylprednisolone or equivalent for any treatment other than the diagnosis of cGVHD within 7 days of randomization.
- 12. Participants on mechanical ventilation or requiring oxygen support or FEV1 < 30%.
- 13. History or current diagnosis of cardiac disease indicating significant risk of safety for participation in the study, such as uncontrolled or significant cardiac disease, including any of the following:
 - a. Recent myocardial infarction (within 6 months before randomization).
 - b. New York Heart Association Class III or IV congestive heart failure.

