4.1.3. Baseline Value

Baseline is the last nonmissing measurement obtained before the first administration of study treatment (eg, itacitinib with corticosteroids or corticosteroids only). When itacitinib and corticosteroids are started on different days, then the rules mentioned in Section 4.1.1 will be followed.

When scheduled assessments and unscheduled assessments occur on the same day, and time of the assessment or time of first dose is not available, use the following convention to determine baseline:

- If both a scheduled and an unscheduled visit are available on the day of the first dose and the time is missing, use the scheduled assessment as baseline.
- If all scheduled assessments are missing on the day of the first dose and an unscheduled assessment is available, use the unscheduled assessment as baseline.

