4.2.3. Prior and Concomitant Medication

Prior medication is defined as any nonstudy medication started before the first dose of itacitinib or corticosteroids for participants on corticosteroids only in the Part 1 expansion.

Concomitant medication is defined as any nonstudy medication that is started accordingly:

- Before the date of first administration of itacitinib or corticosteroids only and is ongoing throughout the study or ends on/after the date of first itacitinib or corticosteroid administration.
- On/after the date of first administration of itacitinib or corticosteroids only and is ongoing or ends during the course of itacitinib or corticosteroid treatment.

A prior medication could also be classified as "both prior and concomitant medication" if the end date is on or after the first dose of itacitinib or corticosteroids only. Since corticosteroids are part of the study medication, they will not appear in the list of prior and concomitant medications unless prescribed for an indication other than GVHD. In the listing, it will be indicated whether a medication is prior only, concomitant only, or both prior and concomitant.

For the purposes of analysis, all medications will be considered concomitant medications unless the medications can unequivocally be defined as not concomitant.

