7.1. General Considerations

In Part 1, all efficacy analyses will be performed using the safety run-in population. In Part 1 Expansion, all efficacy analyses will be performed using the safety population.

If there are not sufficient data for meaningful statistical inference, the planned analysis will not be performed, and only related summary statistics and/or listings will be provided.

In all efficacy analyses, initiation of new systemic anti-GVHD therapy includes 4 scenarios:

1. Initiation of new anti-GVHD therapy including a higher dose of corticosteroid than that used at Day 1.
2. The need for a second dose increase in corticosteroids.
3. A dose increase in corticosteroids that is not tapered back to the previous dose of corticosteroids within 6 weeks (\pm 2 days) of the increase.
4. Reintroduction of systemic corticosteroids that occurs after complete taper of corticosteroids due to response.

No formal statistical tests will be performed.

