7.3.9. Other Efficacy Analyses

The proportion of participants with $\geq 50\%$ reduction in daily corticosteroid dose at Day 180 will be summarized. Corticosteroid dose on study Day 1 will be defined as the starting dose as appropriate.

The proportion of participants successfully tapered off all corticosteroids at Day 180 will be summarized.

Both time to failure-free survival and average biweekly weight-standardized steroid up to Month 6 will be plotted.

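### SAP 4.1.1 dates Day 1 in Group D from the first recorded steroid dose, with no limit at randomization, so the Day 1 steroid reference can follow a different rule in the comparator arm

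*SAP*

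**What the plan says.** SAP 4.1.1 dates Day 1 from the first itacitinib dose, but adds: "For the corticosteroids-only group, Day 1 will be defined as the first nonmissing dose day". Nothing limits this to doses given on or after randomization. Protocol 8.1.2 treats the day of randomization as Day 1 in every arm. SAP 11.1, which lists departures from the protocol, does not mention the difference.

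Several rules depend on Day 1:

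- **Study day** (SAP 4.1.2) is counted from it.
- **Baseline** (SAP 4.1.3) is the last value before the first study treatment, and "When itacitinib and corticosteroids are started on different days, then the rules mentioned in Section 4.1.1 will be followed".
- **The steroid-reduction endpoint** (SAP 7.3.9): "Corticosteroid dose on study Day 1 will be defined as the starting dose as appropriate".
- **The new-therapy rule** (SAP 7.1, scenario 1) counts "Initiation of new anti-GVHD therapy including a higher dose of corticosteroid than that used at Day 1". Under SAP 7.3.1, new therapy at or before the timepoint makes a participant a nonresponder.

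The protocol lets people enter already on steroids. Exclusion 2 removes only a person who "Has received more than 3 days/72 hours of systemic corticosteroid treatment for cGVHD", so up to 72 hours is allowed. The note to inclusion 2 also makes eligible "Candidates who transition from active aGVHD to cGVHD without tapering off of corticosteroids", and gives a level below 0.25 mg/kg per day of methylprednisolone. On where such steroids are reported, SAP 4.2.3 says: "Since corticosteroids are part of the study medication, they will not appear in the list of prior and concomitant medications", except when they are given for something other than GVHD.

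**The concern.** Take two participants with the same steroid history, one randomized to Group A and one to Group D. In Group A, a steroid started before randomization does not move Day 1. In Group D it can, because that dose may be the first one recorded. The two then have different study-day counts, different derived baselines for items such as laboratory values and vital signs, and possibly different steroid reference doses.

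Group D is the only comparator in the Part 1 expansion. Its Month 6 response rate enters the exploratory CMH tests and the posterior probabilities in SAP Table 3, which may support the choice of the Part 2 dose. Its Day 180 steroid results are the control for the tapering endpoints. A reference dose set differently in this one arm could shift those contrasts for reasons unrelated to treatment.

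**Working it through.** The plan gives no figure to reproduce. The check applies the SAP's own rules to matched participants.

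**1. Shift in days.** Inputs: up to 3 days of cGVHD steroid before randomization (Protocol 5.2); treatment starts 0 to 2 days after randomization (Protocol 8.1.2); study day = date − Day 1 date + 1 (SAP 4.1.2). Count randomization as calendar day 0, so Day 180 falls on the Day 1 date + 179.

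- Group D, steroid started 3 days before: −3 + 179 = day 176.
- Itacitinib group, first dose on day 0 to 2: 0 + 179 to 2 + 179 = day 179 to 181.
- Gap: 3 to 5 days. With no prior steroid, and Group D's first dose on the day of randomization, it is 0 to 2 days.

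For carry-over steroid the documents give no duration. Assuming 14 to 28 days of earlier use, the gap is 14 + 0 to 28 + 2, or 14 to 30 days.

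**2. Reference dose.** Protocol 6.1.2 converts prednisone to methylprednisolone by multiplying by 0.80. A carry-over dose at the 0.25 mg/kg limit is 0.25 / 0.80 = 0.3125 mg/kg prednisone. The protocol expects cGVHD steroid to start at 0.5 to 1.0 mg/kg prednisone.

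- *New-therapy rule.* Both 0.5 and 1.0 exceed 0.3125. If the carry-over dose is Group D's Day 1 dose, the participant's initial cGVHD treatment satisfies scenario 1 of SAP 7.1, and SAP 7.3.1 gives nonresponse. A matched Group A participant whose cGVHD dose is in place at the first itacitinib dose does not satisfy it.
- *Reduction endpoint.* Assume a 1.0 mg/kg start and 0.3 mg/kg at Day 180. Against the start the reduction is 1 − 0.3/1.0 = 70% (met). Against the carry-over dose it is 1 − 0.3/0.3125 = 4% (not met).

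**3. Possible effect on Group D's Month 6 rate.** The number affected is not stated. Assume 2 to 7 of 35 (about 5% to 20%), half of whom would otherwise respond: 2/35 × 0.5 = 2.9 points; 7/35 × 0.5 = 10 points.

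**4. What one responder is worth.** In SAP Table 3 with 27 itacitinib responders, going from 21 to 20 responders in Group D raises the posterior from 54.9% to 64.7%. Across the table one step is worth 2.9 points (92.6% to 95.5%) to 10.2 points (44.7% to 54.9%).

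**The case against.** The strongest objection is that an early Group D Day 1 is inferred. SAP 4.2.3 governs a medication listing; it does not say where the CRF stores doses. Protocol 6.3 has prior medication from the 28 days before first dose recorded in the eCRF, so pre-study steroid may sit in a separate record. Protocol 6.1 has participants randomized and then starting treatment on Day 1. SAP 6.4 provides for steroid taken before Day 1, a case that could not arise in Group D if Day 1 were the first steroid dose ever recorded. These passages suggest that post-randomization dosing was intended. The point therefore stands only as a conditional one: the CRFs are not available, the rule as written has no limit, and SAP 6.4 covers exposure duration only and refers back to 4.1.1.

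A reader might infer that organ scoring in Group D falls back to a screening assessment. The documents do not support that. Protocol Table 4, footnote f, says organ and severity scoring "will be performed on Day 1, and this will be the baseline for cGVHD response assessment"; Protocol 8.2.2 has the treating physician compare against that visit; and SAP 6.1.2 uses the Day 1 assessment for baseline organ involvement.

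A reader might also infer that the error always favours itacitinib. That holds only for the low carry-over dose. A pre-steroid baseline in 72-hour starters could favour Group D. Exclusion 11 caps other steroid use only within 7 days of randomization, so an older recorded dose could be higher than 0.25 mg/kg, which would push the reference the other way.

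Finally, for 72-hour starters the shift of at most 5 days lies inside the ±7-day window of the Day 180 visit, and the words allowing discretion in SAP 7.3.9 leave room for a sensible choice of reference. Both points stand. Neither settles scenario 1 of SAP 7.1.

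**Conclusion.** The SAP states two anchors for Day 1, and the one for the comparator is not limited to doses from randomization onward. If steroid doses before randomization are in the exposure data, study-day labels and derived baselines shift in Group D only. The steroid reference in SAP 7.1 and 7.3.9 then follows a different rule there. The reference dose is the part that matters: read literally, a Group D participant who moved from acute to chronic GVHD on a carry-over dose at or below the limit is counted as a nonresponder.

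The fall of about 3 to 10 points in Group D's Month 6 rate rests on an assumed 2 to 7 affected participants and an assumed 50% response among them. It is an illustration, not an estimate.

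Severity is moderate. It would be tempting to say that the dose decision depends on this, but the Part 1 expansion has no formal efficacy test, the CMH tests are exploratory, and SAP 7.2 bases dose selection primarily on adverse events. Time to response, OS, NRM and time to relapse run from randomization, so the Day 1 anchor does not move their start.

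**What to change.** Three short changes to the SAP:

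- **4.1.1:** define Day 1 in Group D as the date of the first corticosteroid dose on or after randomization, tied to the protocol Day 1 visit. For the matched pair above, the remaining gap is then only the 0 to 2 days allowed before the first itacitinib dose.
- **4.1.3:** cross-refer to the protocol Day 1 visit as the cGVHD response baseline in all groups.
- **7.1 and 7.3.9:** state one rule, the same in every group, for which recorded dose is the Day 1 steroid reference, and reconcile it with Protocol 6.1.2.4 and 7.1.1. Moving the date alone is not enough, because a carry-over dose and the new cGVHD dose can fall on the same or adjacent days.

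SAP 11.1 should record any difference from the protocol's Day 1 that remains. The cost is a few sentences; no new data are needed. Before the analysis, the sponsor should also check whether the steroid exposure dataset holds doses dated before randomization and, if so, how many participants have them in each group.

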4.1.2. Study Day

If a visit/reporting date is on or after Day 1, then the study day at the visit/reporting date will be calculated as

$$\text{Day \#} = (\text{visit/reporting date} - \text{Day 1 date} + 1).$$

If the visit/reporting date is before Day 1, then the study day at the visit/reporting date will be calculated as

$$\text{Day \#} = (\text{visit/reporting date} - \text{Day 1 date}).$$

A study day of -1 indicates 1 day before Day 1.

4.1.3. Baseline Value

Baseline is the last nonmissing measurement obtained before the first administration of study treatment (eg, itacitinib with corticosteroids or corticosteroids only). When itacitinib and corticosteroids are started on different days, then the rules mentioned in Section 4.1.1 will be followed.

When scheduled assessments and unscheduled assessments occur on the same day, and time of the assessment or time of first dose is not available, use the following convention to determine baseline:

- If both a scheduled and an unscheduled visit are available on the day of the first dose and the time is missing, use the scheduled assessment as baseline.
- If all scheduled assessments are missing on the day of the first dose and an unscheduled assessment is available, use the unscheduled assessment as baseline.

